6.3 Withdrawal criteria

Subjects are free to withdraw from the study at any time, without prejudice to their continued care.

Subjects should be withdrawn from the study if any of the following events occur:

1. Subject develops an illness that would interfere with his/her continued participation.
2. Subject is noncompliant with the study procedures or medications in the opinion of the Investigator.
3. Subject considered as having either a suspected new latent or who develop active TB or NTMB infection during the study (including but not limited to, conversion demonstrated by IGRA or other diagnostic means) must be immediately discontinued from study medication, and an Early Termination Visit must be scheduled as soon as possible, but not later than the next regular visit.

Confirmed active TB is a serious adverse event (SAE) and must be captured on an SAE report form and provided to the Sponsor in accordance with SAE reporting requirements. As with all SAEs, periodic follow-up reports should be completed as per protocol requirements until such time as the TB infection resolves.

Subjects who prematurely discontinue treatment for latent TB, or, in the opinion of the Investigator or Sponsor, are noncompliant with anti-TB therapy must discontinue further use of study medication and be immediately withdrawn.

4. There is confirmation of a positive HBV-DNA assay during the study period, subject with positive HBc antibody and/or HBs antibody at Screening. Appropriate actions such as administration of a nucleic acid analog should be taken after prompt consultation with a hepatologist.
5. Subjects developing aggravation of the primary disease or concomitant disease with hospitalization in the opinion of the Investigator.
6. Subjects with generalized pustular PSO developing a total score on the JDA Severity Index for Generalized Pustular PSO ≥ 14 at any post-Baseline visit.
7. Subject withdraws his/her consent.
8. There is confirmation of a subject pregnancy during the study, as evidenced by a positive pregnancy test.
9. The Sponsor or a regulatory agency requests withdrawal of the subject.
10. Subjects develops guttate PSO.

Once withdrawn from study treatment, subjects must return for the Early Withdrawal Visit and complete all Early Withdrawal assessments, and complete a final Safety Follow-Up Visit 10 weeks after the last dose of study medication.

Investigators should attempt to obtain information on subjects in the case of withdrawal or discontinuation. For subjects considered as lost to follow up, the Investigator should make an effort (at least 1 phone call and 1 written message to the subject), and document his/her effort (date and summary of the phone call and copy of the written message in the source documents), to complete the final evaluation. All results of these evaluations and observations, together with a narrative description of the reason(s) for removing the subject, must be recorded in the source documents. The Case Report form must document the primary reason for withdrawal or discontinuation.

Investigators should contact the Medical Monitor, whenever possible, to discuss the withdrawal of a subject in advance.

Subjects withdrawn from the study will not be replaced.

6.3.1 Potential drug-induced liver injury IMP discontinuation criteria

Subjects with potential drug-induced liver injury (PDILI) must be assessed to determine if IMP must be discontinued. In addition, all concomitant medications and herbal supplements that are not medically necessary should also be discontinued.

The PDILI criteria below require immediate and permanent discontinuation of IMP:

- Subjects with either of the following:
 - ALT or AST \geq 8xULN
 - ALT or AST \geq 3xULN and coexisting total bilirubin \geq 2xULN

The PDILI criterion below requires immediate discontinuation of IMP:

- Subjects with ALT or AST \geq 3xULN who exhibit temporally associated symptoms of hepatitis or hypersensitivity. Hepatitis symptoms include fatigue, nausea, vomiting, right upper quadrant pain or tenderness. Hypersensitivity symptoms include fever (without clear alternative cause), rash, or eosinophilia (ie, $>$ 5%).

The PDILI criterion below allows for subjects to continue on IMP at the discretion of the Investigator.

- Subjects with ALT or AST \geq 3xULN (and $>$ 2x baseline) and $<$ 8xULN, total bilirubin $<$ 2xULN, and no eosinophilia (ie, \leq 5%), with no fever, rash, or symptoms of hepatitis (eg, fatigue, nausea, vomiting, right upper quadrant pain or tenderness).

Evaluation of PDILI must be initiated as described in [Section 12.2.1](#). If subjects are unable to comply with the applicable monitoring schedule, IMP must be discontinued immediately.

Investigators should attempt to obtain information on subjects in the case of IMP discontinuation to complete the final evaluation. Subjects with PDILI should not be withdrawn from the study until investigation and monitoring are complete. All results of these evaluations and observations, as well as the reason(s) for IMP discontinuation and subject withdrawal (if applicable), must be recorded in the source documents. The CRF must document the primary reason for IMP discontinuation.

7 STUDY TREATMENTS

7.1 Description of investigational medicinal products

The investigational medicinal products (IMPs) used in this study are CZP and PBO. These products will be supplied by the UCB Clinical Supply Unit. Drug and supplies will consist of the following:

Certolizumab pegol is supplied as a sterile, clear, colorless to slightly yellow liquid solution with a pH of approximately 4.7 in 1mL single use glass prefilled syringe (PFS) with a 25G ½-inch thin-wall needle for sc injection. Each syringe contains an extractable volume of 1mL at a

concentration of 200mg/mL of CZP in 10mM sodium acetate buffer and 125mM sodium chloride as a tonicity agent.

Placebo is supplied in a PFS with a 25G ½-inch thin-wall needle, containing an injectable volume of 1mL 0.9% saline for single use. Due to the difference in presentation and viscosity between CZP and PBO, special precautions will be taken in order to ensure maintained blinding of the study (unblinded/blinded site personnel and monitors).

7.2 Treatments to be administered

The study medication is to be administered every 2 weeks by sc injections.

Study injections will be administered by study site staff. Suitable areas for sc injections are the upper arm, lateral abdominal wall, and upper outer thigh. During each dosing visit if 2 injections are being administered, each of the 2 injections should be administered at a separate injection site.

Injections should be administered with a minimum of 10 days between study injections. Each deviation less than these minimum timeframes must be discussed immediately with the Medical Monitor.

A pharmacy manual will be provided to each site containing instructions regarding drug preparation and dosing.

7.3 Packaging

Certolizumab pegol and PBO are packaged and labelled according to Good Manufacturing Practice (GMP) guidelines and applicable laws or regulations. They are suitably packaged in such a way as to protect the IMPs from deterioration during transportation and storage.

7.4 Labeling

Clinical drug supplies will be labeled in accordance with the current International Council for Harmonisation (ICH) guidelines on Good Clinical Practice (GCP) and GMP and will include any locally required statements. If necessary, labels will be translated into the local language.

7.5 Handling and storage requirements

Investigational medicinal product (IMP) must be stored under the conditions defined in the IMP Handling Manual.

The Investigator (or designee) is responsible for the safe and proper storage of IMP at the site. Investigational medicinal product stored by the Investigator is to be kept in a secured area with limited access.

Appropriate storage conditions must be ensured by controlled temperature and by completion of a temperature log in accordance with local requirements on a regular basis, per Study Manuals, showing minimum and maximum temperatures reached over the time interval.

Study drug will be shipped to the study sites in temperature controlled containers. Out-of-range shipping or storage conditions must be brought to the attention of the Sponsor or designee, immediately. Authorization to use any out-of-range IMP must be documented and received prior to dispensing or administering the IMP at the study site.

7.6 Drug accountability

A Drug Accountability form will be used to record IMP dispensing and return information on a by-subject basis and will serve as source documentation during the course of the study. Details of any IMP lost, damaged (due to breakage or wastage), not used, partially used, disposed of at the study site, or returned to the Sponsor or designee must also be recorded on the appropriate forms. All supplies and pharmacy documentation must be made available throughout the study for UCB (or designee) to review.

All study drug documentation (eg, shipping receipts, drug accountability logs, IRT randomization materials) must be maintained and accessed by unblinded, trained site personnel only. Designated, unblinded site personnel must be appropriately trained and licensed (per country guidelines) to administer injections.

Blinded study staff may be delegated the responsibility to receive, inventory and destroy the used kits. The packaging identifies each kit by a unique number that does not correlate to the contents and therefore, does not unblind study site staff. Unblinded study staff will be responsible for preparation (breaking tamper proof sticker on kit, etc) and administration of the clinical trial material to the subject, including recording the administration information on source documents.

The Investigator (or designee) is responsible for retaining all used, unused, and partially used containers of IMP until returned or destroyed.

The Investigator may assign some of the Investigator's duties for drug accountability at the study site to an appropriate pharmacist/designee.

The Investigator must ensure that the IMP is used only in accordance with the protocol.

Periodically, and/or after completion of the clinical phase of the study, all used (including empty containers)/partially used, unused and unused IMP containers must be reconciled and returned to the Sponsor, or designee, preferably in their original package. Onsite destruction of used kits only may be allowed with prior approval from the Sponsor or designee after reconciliation.

7.7 Procedures for monitoring subject compliance

Study medication will be administered in the clinic and compliance will be determined at the visit by study personnel. Drug accountability must be recorded on the Drug Accountability form.

If a subject is found to be persistently noncompliant (missing 2 or more doses during the first 16 weeks of treatment and missing 3 or more doses from Week 16 thereafter), the Sponsor, in conjunction with the Investigator, will make a decision as to whether the subject should be withdrawn from the study.

7.8 Concomitant medications/treatments

All medications (including over-the-counter drugs, vitamins, antacids) being taken at the time of the Baseline Visit or during study participation will be collected and recorded on the eCRF.

Medication entries should be specific to the generic name (if a combination drug, then marketed product name) and will include the dose, unit, and frequency of administration and/or treatment, route of administration, start date, discontinuation date, and indication.

The Investigator should examine the acceptability of all concomitant procedures, medications, topical preparations, and dietary supplements not explicitly prohibited in this study.

In order to ensure that appropriate concomitant therapy is administered, subjects will be instructed to consult with the Investigator prior to taking any medication (either self-administered nonprescription drugs or prescription therapy prescribed by another physician).

7.8.1 Permitted concomitant treatments (medications and therapies)

The use of concomitant medications for medical conditions (eg, hypertension, diabetes, acute infections) or treatment of an AE is permitted during this study as long as medications are not explicitly prohibited by the protocol. The following concomitant medication is permitted during the study:

- NSAIDs, acetaminophen, paracetamol and opioids for PsA

7.8.1.1 Permitted concomitant treatments (medications and therapies) for subjects with moderate to severe chronic plaque PSO who escape from double-blind treatment

For subjects who escape from double-blind treatment, the following medications are permitted:

- Moderate potency (class III to V) topical corticosteroids for PSO
- Vitamin D analogues and topical retinoids for PSO
- Keratolytic and coal tar for PSO

7.8.1.2 Permitted concomitant treatments (medications and therapies) for subjects with generalized pustular PSO or erythrodermic PSO

The use of systemic retinoids, systemic immunosuppressants agents (eg, methotrexate, cyclosporine, azathioprine), and/or systemic corticosteroids (at a daily dose ≤ 10 mg/day of prednisone or its equivalent) are allowed provided the subject had been using such medication(s) since before starting the study. Dose reduction of these drugs is allowed as well; however, dose increase after dose reduction is limited to the level at the start of the study.

7.8.2 Prohibited concomitant treatments (medications and therapies)

Prohibited concomitant treatments (medications and therapies) differ based on whether the subject is in the moderate to severe chronic plaque PSO, generalized pustular PSO, or erythrodermic PSO treatment group.

7.8.2.1 Prohibited concomitant treatments (medications and therapies) for subjects with moderate to severe chronic plaque PSO

The following concomitant medications are prohibited for subjects with moderate to severe chronic plaque PSO:

- Systemic retinoids
- Systemic treatments for PSO
 - Systemic immunosuppressants agents (eg, methotrexate, cyclosporine, azathioprine, thioguanine)
 - Systemic corticosteroids
 - Phototherapy or chemophototherapy

- Anti-TNFs: infliximab (including biosimilar), adalimumab, golimumab, etanercept
- Other biologics and systemic therapies: ustekimumab, secukinumab, ixekizumab, and brodalumab
- Any other antipsoriatic agent (systemic) under investigation (or approved after the protocol is approved)
- Rituximab
- Topical agents for dermatologic use:
 - High potency topical corticosteroids (class I and II)
 - Any other antipsoriatic agent (topical) under investigation (or approved after the protocol is approved)
 - Moderate potency (class III to V) topical corticosteroids
 - Vitamin D analogues and topical retinoids
 - Keratolytic and coal tar

7.8.2.2 Prohibited concomitant treatments (medications and therapies) for subjects with generalized pustular PSO or erythrodermic PSO

The following concomitant medications are prohibited for subjects with generalized pustular PSO or erythrodermic PSO:

- Systemic treatments for PSO
 - Phototherapy or chemophototherapy
 - Granulocyte and monocyte adsorption apheresis
 - Anti-TNFs: infliximab (including biosimilar), adalimumab, golimumab, etanercept
 - Other biologics and systemic therapies: ustekimumab, secukinumab, ixekizumab, and brodalumab
 - Any other antipsoriatic agent (systemic) under investigation (or approved after the protocol is approved)
 - Antipsoriatic agent (topical) under investigation (or approved after the protocol is approved)
 - Rituximab

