Escape Arm in Maintenance Period (Final Analysis, including data after escape for subjects who escaped at/after Week 16)

Observed PASI50, PASI75, PASI90 and PASI100 responder rates will be summarized by the treatment group before escape from Week 16 to Week 52 based on EM FAS. Observed results in maintenance period but before escape will not be included in this table.

Additionally, the observed PASI50, PASI75, PASI90 and PASI100 responder rates will be summarized by the treatment group before escape and by escape maintenance treatment group from Week 16 to Week 52 based on EM FAS. Due to up-titration, subjects may be presented in both escape maintenance treatment groups (Esc CZP 200mg Q2W, Esc CZP 400mg Q2W), so that the sum of the sample sizes of both treatment groups will exceed the number of escapers.

Combined Initial and Maintenance Period (Interim Analysis, excluding subjects who escaped at Week 16)

PASI50, PASI75, PASI90 and PASI100 responder rates will be summarized by randomized treatment group at each visit from Week 0 to Week 24 based on NRI and observed case data. Responder rates based on NRI data, odds ratios with corresponding 95% CIs will be derived without modelling but only by calculating counts, percentages and CIs. No p-values will be presented. For the NRI summary, subjects will be imputed as non-responders at the point of escape or for those subjects who do not escape, from the point of premature withdrawal through Week 24. For observed data, no imputation will be performed and counts and percentages of responders will be presented.

Combined Initial and Maintenance Period (Final Analysis, including subjects who escaped at/after Week 16)

PASI50, PASI75, PASI90 and PASI100 responder rates will be summarized by randomized treatment group at each visit from Week 0 to Week 52 based on NRI and observed case data. Responder rates based on NRI data will be derived without modelling but only by calculating counts and percentages. No p-values will be presented. For the NRI summary, subjects will

be imputed as non-responders at the point of escape or for those subjects who do not escape, from the point of premature withdrawal through Week 52. For observed data, no imputation will be performed and counts and percentages of responders will be presented.

Additionally, the same table will be produced at each visit from Week 0 to Week 52 based on FAS by the following groups:

- PBO

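### Protocol 7.8.1.1 permits, and 7.8.2.1 prohibits, the same topical agents after escape, and the escape-arm PASI and PGA tables do not show who used them

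*Protocol*

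**What the plan says.** Protocol 7.8.1.1, on plaque subjects who leave double-blind treatment, reads: "For subjects who escape from double-blind treatment, the following medications are permitted". Three items follow: "Moderate potency (class III to V) topical corticosteroids for PSO", "Vitamin D analogues and topical retinoids for PSO" and "Keratolytic and coal tar for PSO".

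Protocol 7.8.2.1 opens with "The following concomitant medications are prohibited for subjects with moderate to severe chronic plaque PSO". Its list of topical agents contains the same three items. It also names class I and II corticosteroids, which no section permits.

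On the analysis side, SAP 8.3.1 states: "Observed PASI50, PASI75, PASI90 and PASI100 responder rates will be summarized by the treatment group before escape". This covers Weeks 16 to 52, and the rates are then split further by escape dose group. SAP 8.3.2 does the same for PGA response. SAP 6.4 summarises concomitant medications for the Maintenance Period, and SAP 5.2 tabulates important deviations in that period by escape group. Neither output is linked to response.

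**The concern.** Two live rules govern the same agents in the same subjects and point in opposite directions. An investigator who reads 7.8.1.1 may add a topical at escape. One who reads 7.8.2.1 will withhold it or log its use as a deviation.

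Two outputs depend on which section is read:

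- **Deviation counts by escape group.** Identical conduct may be counted at one site and not at another.
- **Escape-arm PASI and PGA rates.** These are listed variables (Protocol 4.1.3.1.4) and bear on the long-term efficacy objective (Protocol 3.3). Protocol 14.3 expects most placebo subjects to move to CZP at Week 16, so for many of them this is their first CZP data.

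The plan itself treats these agents as able to affect skin disease: Table 6-1 requires plaque subjects to be off them for 2 weeks before Baseline. As the SAP stands, a reader of the escape response tables cannot see how much topical treatment accompanied CZP.

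**Working it through.** The plan gives no figure for topical use after escape, so there is none to reproduce. The check is a comparison of texts, followed by a bound on how many subjects fall under the conflict.

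**1. Do the lists overlap?**

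| Agent | 7.8.1.1 (escapers) | 7.8.2.1 (plaque subjects) |
|---|---|---|
| Corticosteroids, class III to V | permitted | prohibited |
| Vitamin D analogues, topical retinoids | permitted | prohibited |
| Keratolytics, coal tar | permitted | prohibited |
| Corticosteroids, class I and II | not listed | prohibited (no conflict) |

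The permitted items carry the qualifier that use is for psoriasis. The prohibited ones sit under agents for dermatologic use, which includes psoriasis, so the wording does not separate them.

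**2. Does any text settle which rule prevails?** Neither section refers to the other, and 7.8.2.1 has no time limit. Protocol 7.8 leaves to the Investigator's judgement only treatments that are not explicitly prohibited, and these are. The history of the text does not help as evidence of intent. Amendment 4 gives as a purpose that the prohibitions run through the whole study, yet it also sharpened the heading of 7.8.1.1 and left the permission in place.

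**3. Which outputs can be touched?**

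- *Week 16 tests:* no. Escape starts at Week 16 at the earliest, and that visit's assessments precede dosing (Protocol 8.10).
- *Per-protocol set:* no. Deviations that exclude a subject from it matter only in the Initial Period (SAP 5.2).
- *Blinded-maintenance tables:* no. After escape, subjects count as non-responders or have the escape-visit value carried forward (SAP 4.2).
- *Post-escape observed rates:* yes. This means the escape tables in SAP 8.3.1 and 8.3.2 and the observed post-escape data in the escape columns of the combined-period tables.
- *Maintenance Period deviations by escape group:* yes.

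**4. How many subjects fall under the conflicting rules?** The documents give no PASI50 rates. A subject without PASI50 is also without PASI75, so the PASI75 rates assumed in Protocol 14.8.1 (15% placebo, 70% CZP 200mg, 75% CZP 400mg) give a ceiling for expected Week 16 escapers:

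- placebo: 25 × 0.85 = 21.25
- CZP 200mg: 50 × 0.30 = 15
- CZP 400mg: 50 × 0.25 = 12.5
- total: 48.75, about 49 of 125 (39%)

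With assumed PASI50 rates (not in the documents) of 20% to 40% on placebo and 85% to 90% on CZP, the count is 25 × (0.60 to 0.80) = 15 to 20, plus 100 × (0.10 to 0.15) = 10 to 15. That is 25 to 35 of 125 (20% to 28%). Escapes at Weeks 24, 32 and 40 would add to either figure.

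**5. How far could the observed rate move?** If a share u of escapers uses a topical and use adds d to their response rate, the escape-arm rate rises by u × d. Neither quantity is in the documents. For an assumed d of 5 to 20 percentage points:

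| u | Rise in observed rate (points) |
|---|---|
| 0 | 0 |
| 50% | 2.5 to 10 |
| 100% | 5 to 20 |

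**The case against.** The best defence is that 7.8.1.1 is the specific rule and should be read as an exception to a general list. That reading is possible, but nothing in the text states it, and step 2 shows evidence on both sides. Divergent site practice is therefore an inference from two opposite rules, not something the documents report.

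Several stronger readings are tempting and should not be drawn:

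- **Section 7.8.1 already settles it.** The clause "as long as medications are not explicitly prohibited by the protocol" might be taken as giving the prohibited list precedence. Its sentence concerns medicines for other medical conditions or for adverse events, so it does not rank 7.8.2.1 over 7.8.1.1.
- **Subjects will be withdrawn over it.** Criterion 2 in Protocol 6.3 reads "Subject is noncompliant with the study procedures or medications in the opinion of the Investigator". It turns on the Investigator's own view, and an Investigator who agreed to a topical is unlikely to call its use noncompliance. Dose increase and withdrawal for lack of benefit after escape are discretionary in any case.
- **Every escaper is affected.** All fall under the conflicting rules. Response can change only in those who use a topical, and that number may be zero.
- **Escape response cannot be attributed to CZP because of this.** The escape arm is open-label without a concurrent control, so attribution is limited under either rule. If topicals were clearly permitted, the mixing would remain.
- **The SAP ignores topical use.** It summarises concomitant medications and deviations. Only the link to response is missing.

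It is also fair to say that the stakes are modest: these are other efficacy variables, reported descriptively, and no hypothesis test changes.

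**Conclusion.** The contradiction is in the current text and holds for class III to V topical corticosteroids, vitamin D analogues, topical retinoids, keratolytics and coal tar. It does not extend to class I and II corticosteroids.

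Its consequence is limited to deviation counts that may not mean the same thing across sites, and to escape-arm PASI and PGA rates that may include topical treatment. At most about 49 of 125 subjects are expected to come under the conflicting rules at Week 16, if the protocol's PASI75 assumptions hold; 25 to 35 is a plausible count under the assumed PASI50 rates. The shift in the observed rates cannot be estimated from the documents and starts at zero.

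A reader might infer that the trial's efficacy conclusion is at risk. It is not, for the reasons in step 3.

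**What to change.** 1. **Protocol 7.8.1.1 and 7.8.2.1:** reconcile them so that one statement governs these agents after escape. Which rule applies is for the clinical team. Align the important-deviation criteria with it.
2. **SAP 8.3.1 and 8.3.2:** in the observed escape-arm tables, show per column and visit the number of escape subjects who have started a topical antipsoriatic. The medication, indication and start date are already collected (Protocol 7.8), and the partial-date rules in SAP 6.4 can be reused.
3. **Supplementary sensitivity display:** repeat the response rates with visits after topical start counted as non-response. Keep the observed rates as the main presentation, because this display would score topical use as failure even if the clinical team decides that it is permitted.

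The cost is a short protocol clarification and one extra descriptive display. The sensitivity rates may look slightly lower than the observed ones.
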